All study assessments will be programmed in the electronic medical record (Epic EMR) with the help of the epic physician builder who is co-investigator on the study ([name] [name], MD). Demographics, key comorbidities (cardiovascular disease, hypertension, diabetes, obesity, osteoporosis, thromboembolic disease, cancer), routine laboratories including inflammatory markers, and disease characteristics will be updated **at every visit**. Information that does not change such as disease onset for psoriasis and psoriatic arthritis will be recorded only at baseline. Study visits will occur at 3-4 month intervals in conjunction with clinical care. Disease assessments will comprise physician assessments (Table 1 a,b), laboratories (Table 2), and patient reported outcomes (Table 3 a,b). Medication doses and changes in medications will be recorded longitudinally. Disease activity measures will be programmed in the medical record such that scores are automatically generated from the primary data elements as illustrated in Table 4.

Table 1a. Physician assessments

PsA Phenotype smartform	Elements
CASPAR classification criteria (cumulative)	Psoriasis (active, history, family history), Nail psoriasis, Dactylitis, Negative rheumatoid factor, Juxtaarticular new bone (radiographic PsA)
Extraarticular manifestations (cumulative)	Uveitis, Inflammatory bowel disease, Inflammatory back pain, Psoriasis type (plaque, pustular, inverse, guttate, erythrodermic) and special locations (scalp, palmoplantar, intergluteal cleft/perianal), Elevated CRP
Comorbidities (from problem list)	Cancer of skin (not melanoma), Melanoma skin cancer, Cancer other than skin (fill in), Coronary artery disease, Diabetes, Fatty liver disease, Obesity , Osteoporosis, Stroke, Thyroid disease, Vitiligo

Table 1b. Disease activity measures

Psoriatic arthritis areas/domains	Physician assessments
Musculoskeletal Arthritis	Tender/swollen joint counts 66/68
Dactylitis	Dactylitis index (LDI basic) (0-20)
Enthesitis	Enthesitis index (SPARCC) (0-18)
Spondyloarthritis	Antropometrics (Cervical range of motion anteroposterior and lateral: occiput to wall, degrees lateral rotation; Thoracic expansion; Lumbar spine: Schober 10 and 15 cm, Lateral lumbar flexion)*

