Skin and nails	Psoriasis body surface area affected (BSA%); Psoriasis location (scalp, upper extremities, lower extremities, torso, abdomen); Psoriasis phenotype (plaque, pustular, inverse, guttate, erythrodermic) Investigator global assessment (0-4); Nail disease (pitting, onycholysis, and surface area affected)

* assessed only at baseline

Table 2. Laboratory assessments

Psoriatic arthritis areas/domains	Laboratory test
Inflammatory markers	C reactive protein (CRP, mg/dL), ESR

We will also assess complete blood counts and comprehensive metabolic panel at every visit as part of usual clinical care. We will retrospectively abstract serologic information collected as part of usual clinical care from the medical record (rheumatoid factor, anti-cyclic citrullinated peptide (anti-CCP) status, HLA-B27, and ANA).

Table 3a. Patient reported treatment success impression

The final questions will be refined with patient research partners to make sure these are formulated such that patients understand we are assessing at each visit whether they have achieved their personal treatment goals for their psoriatic arthritis.

Patient impression of PsA treatment goals met	Response options
1. "Today, considering the level of control of your psoriatic arthritis and psoriasis, do you consider your treatment has been successful?"	1. yes 2. no
2. "If in your opinion, psoriatic arthritis and psoriasis treatments have NOT been successful for you, please choose the three most important manifestations and life impact aspects that are still active for you (from your psoriatic arthritis and psoriasis)."	1. inflamed joints, 2. inflamed tendons, 3. back/spine inflammation, 4. skin psoriasis, 5. nail psoriasis, 6. scalp psoriasis, 7. Pain, 8. Fatigue, 9. Stiffness, 10. Ability to be physically active/exercise, 11. Ability to participate with family activities, 12. Ability to work, 13. Ability to participate in social activities, 14. Emotional impact, 15. Ability to be independent in my daily activities, 16. Other, please fill in.

Patient impression of PsA treatment goals met	Response options
3. Patient acceptable symptom state: "If you were to remain for the next few months as you were during the past week, would this be acceptable or unacceptable for you?"	1. acceptable 2. unacceptable

Table 3b. Patient reported outcomes for disease status and life impact

Psoriatic arthritis areas/domains	Patient reported outcomes

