Safety assessments: All adverse events (AE) will be recorded and managed per usual clinical care. Serious adverse events (SAE) are defined as adverse events that meet any of the following criteria: result in death; are life-threatening (i.e., in the opinion of the Investigator(s) the subject is at immediate risk of death from the AE); require inpatient hospitalization or prolongation of existing hospitalization; result in persistent or significant disability/incapacity (a substantial disruption of the subject's ability to conduct normal life functions); represent a congenital anomaly/birth defect; constitute an important medical event. As part of usual clinical care, some patients participating in the study will be taking apremilast. Any SAE due to apremilast must be reported immediately (i.e., within 24 hours of the Investigators' knowledge of the event) to Amgen Inc Safety by facsimile. A written report (prepared by the Investigator(s) using an SAE Report Form or a 3500A Medwatch form is to be faxed to Safety (see below for contact information).

Amgen Inc Drug Safety Contact Information:

Amgen Inc Corporation
Global Drug Safety and Risk Management
[name]
[name]
[contact]
E-mail: [contact]

Pregnancies: Pregnancies and suspected pregnancies (including a positive pregnancy test regardless of age or disease state) of a female subject or the female partner of a male subject occurring while the subject is on apremilast, or within 30 days of the subject's last dose of study drug, are considered immediately reportable events. Apremilast is to be discontinued immediately. The pregnancy, suspected pregnancy, or positive pregnancy test must be reported to Amgen Inc Safety immediately facsimile using the Pregnancy Report form provided by Amgen Inc.

5. Inclusion/Exclusion Criteria

Inclusion criteria: English speaking/reading adults, ages 18 to 95 years who are patients in the Johns Hopkins Arthritis Center and/or the Psoriatic Arthritis Clinical Program (PI, [name] MD MHS directs the PsA program) and are followed every 3-4 months. Participants have to meet CASPAR classification criteria for psoriatic arthritis (supplementary material), and be able to interact with touch screen computer.

[figure not shown]
Exclusion criteria: None

6. Drugs/ Substances/ Devices – Not Applicable

7. Study Statistics

Grouping of treatment goals met or not met is based on the primary outcome at each study visit (Fig1).

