Figure 1. Determining patient status in terms of treatment goals met (treatment has been successful from the patient's perspective) or not.

a. Predictors of successful treatment/reaching PsA treatment goals (primary outcome) from a patient perspective: In the longitudinal dataset with up to three visits per participant, we will examine predictors of 'treatment goals met' status using logistic regression with covariates disease characteristics and patient reported variables. We will identify predictors associated with a transition state from unmet to met, a stable status of treatment goals met, as well as predictors of stable status of unmet goals or transition in the negative direction (state variable with 4 categories: unmet to met, stable met, stable unmet, met to unmet). Full visits for this study must be in-person so that the physician assessment of the patient's disease is complete.

b. Prevalence of patients reporting successful treatment/they meet PsA treatment goals from their perspective: We will perform exploratory data analysis to estimate the prevalence of 'patient treatment goals met' status in this longitudinal guideline based therapy cohort. We will then compare characteristics of 'treatment goals met' vs 'not met' patient groups using proportions for binary/categorical (chi square tests) and means for continuous variables (t-tests).

c. Frequency and direction of longitudinal transitions between treatment goals met(successful treatment)/not met states: 3 observations/participant Inperson Visits only: We will determine how patient states change over time to define stability of the notion of successful treatment. Interim Telemedicine visit data will be collected to fill gaps between extended in-person intervals.

d. Score ranges that correspond to a status of patients' treatment goals are met (successful treatment) on a set of PsA outcome measures used in the study, including composite disease activity measures: We will calculate average score ranges for multiple variables of interest that correspond to a status of successful treatment for patients.

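### The primary predictor analysis in section 7a does not specify how repeated visits by the same patient are handled or that covariates precede the outcome

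*Combined protocol and SAP*

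**What the plan says.** The opening of section 7 sets the outcome visit by visit: "Grouping of treatment goals met or not met is based on the primary outcome at each study visit". The item behind it, in Table 3a of section 4, is a yes/no question: "Today, considering the level of control of your psoriatic arthritis and psoriasis, do you consider your treatment has been successful".

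Section 7a gives the method for the primary objective. The data are described as follows: "In the longitudinal dataset with up to three visits per participant". Status is to be analysed "using logistic regression with covariates disease characteristics and patient reported variables". The same paragraph then seeks predictors of moving from unmet to met, of "a stable status of treatment goals met, as well as predictors of stable status of unmet goals or transition in the negative direction", and summarises these as a "state variable with 4 categories: unmet to met, stable met, stable unmet, met to unmet".

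Most covariates are refreshed at each visit, but section 4 also says: "Information that does not change such as disease onset for psoriasis and psoriatic arthritis will be recorded only at baseline". Table 1b marks the spinal measurements as taken at baseline alone. Section 7c restricts transitions to in-person visits and adds: "Interim Telemedicine visit data will be collected to fill gaps between extended in-person intervals".

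Sections 7b to 7f add no covariate timing, no method for correlated rows and no contrast for the four states. Figure 1 is not reproduced in the text available. Its caption concerns deciding met or not-met status.

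**The concern.** Two choices that determine what the primary analysis means are left open.

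The first is the error bars. One patient can contribute three rows, and a patient satisfied at one visit is likely to be satisfied at the next. Ordinary logistic regression counts those rows as independent. Covariates that are fixed or slow to change then look better supported than they are, and null covariates are declared predictors too often.

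The second is timing. The outcome is an answer about today, and pain, patient globals and PsAID are patient reports collected at the same visits. Relating them within a visit shows which scores go with feeling successfully treated. It does not show who will get there. The primary objective and the impact statement in the abstract both claim the latter.

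**Working it through.** **No figure to reproduce.** The documents give no sample size, prevalence, transition rate or correlation. All rates below are assumptions that show the mechanism and a plausible range.

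**Inputs.** Three visits per patient (section 7a). Let q be the probability that unmet becomes met by the next visit, and r the probability that met becomes unmet. Assumed (q, r): (0.3, 0.2), (0.2, 0.1), (0.4, 0.3). Status follows a two-state chain in which the next visit depends only on the current one, started at its stationary share.

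**Step 1: outcome correlation.** Visits one apart correlate at 1 − q − r, and visits two apart at its square. Of the three visit pairs, two are adjacent, so the mean is [2(1 − q − r) + (1 − q − r)²]/3.
- (0.3, 0.2): (0.5 + 0.5 + 0.25)/3 = 0.417
- (0.2, 0.1): (0.7 + 0.7 + 0.49)/3 = 0.63
- (0.4, 0.3): (0.3 + 0.3 + 0.09)/3 = 0.23

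**Step 2: variance inflation and error rate.** For a null covariate with within-patient correlation c, the design effect is DE = 1 + 2 × mean correlation × c. The actual two-sided error rate at nominal 5% is 2[1 − Φ(1.96/√DE)].

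| (q, r) | c = 1: DE | c = 1: error rate | c = 0.5: DE | c = 0.5: error rate |
|---|---|---|---|---|
| (0.3, 0.2) | 1.83 | 14.8% | 1.42 | 10.0% |
| (0.2, 0.1) | 2.26 | 19.2% | 1.63 | 12.5% |
| (0.4, 0.3) | 1.46 | 10.5% | 1.23 | 7.7% |

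**Step 3: simulation check.** With 100 patients, three visits, a patient-constant null covariate and 1,500 replicates, ordinary logistic regression rejected in 14.0%, 19.7% and 11.1% of runs, in the same order. Patient-clustered errors gave 4.5%, 4.5% and 5.7%. Separate simulations at c = 0.5 gave about 7% to 13% without clustering.

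**Step 4: does this carry over to transition models?** With separate models by starting state, the unclustered error rate was 4% to 6% under the same chain, even for a constant covariate. In this chain the next status depends only on the current one, so conditioning on the starting state removes the dependence. The inflation therefore belongs to the status model. A real cohort may have persistent patient differences that the chain leaves out, so clustering there is a safeguard.

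**Step 5: timing.** This needs no arithmetic. Outcome and covariates are recorded at the same visits, and the outcome refers to that day. Unless the covariates are taken from an earlier visit, the model describes concurrent association.

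**The case against.** The plan is silent, not wrong in so many words. GEE and mixed models are also logistic regression, and nothing rules out earlier-visit covariates. That is fair, and it is why the error rates above are conditional on an ordinary fit. But this is the only model named for the primary objective, and the open choices lead to different answers.

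Same-visit association may also be partly intended. Secondary objective C asks which scores correspond to goals met, and concurrent data serve that. This stands, so the same-visit model should stay under an accurate label. It does not meet an objective about reaching goals.

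The highest error rates need a covariate that never changes within patient, and many are updated at each visit. This also stands, which is why the range for within-patient correlation 0.5 is given.

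Two stronger readings are tempting:
- **That the four-state outcome ignores starting status and so biases predictors of change.** Such bias can be constructed. Take q = 0.3 in two groups with 50% and 40% starting unmet. Unmet-to-met against all other states has odds ratio (0.15/0.85)/(0.12/0.88) = 1.29, although the covariate has no effect on change. But this needs a contrast that crosses starting states and is then read as change, and the plan states neither. The four states retain starting status. Unmet-to-met against stable unmet gives (0.15/0.35)/(0.12/0.28) = 1.00.
- **That some patients cannot be classified.** Unmet-met-unmet and met-unmet-met fit no label only if a label covers the whole three-visit path. The labels describe two time points, which suggests a visit pair or first-to-last. Which of these is meant is a clarification.

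**Conclusion.** The point holds for two omissions: no handling of within-patient correlation, and no statement that covariates precede the outcome. If the status model is fitted as ordinary logistic regression, false-positive rates at nominal 5% run at about 10% to 20% for patient-constant covariates and about 7% to 13% at within-patient correlation 0.5, against close to 5% with clustered errors. These figures rest on assumed transition rates and a first-order chain with three complete visits, and the size in this cohort cannot be read from the documents. With same-visit covariates, the results are correlates of current status.

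A reader might infer that the four-state analysis is itself invalid, or that the transition models share the inflated error rate. The documents and the calculation support neither. The transition unit and the contrasts need naming, but as part of the same repair.

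**What to change.** Amend section 7a in two parts.

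1. **Status model.** Fit it by GEE or with standard errors clustered on patient, and report same-visit results as correlates of current status.
2. **Reaching or losing goal.** Define transitions on consecutive in-person pairs (visits 1 to 2 and 2 to 3). Take covariates from the visit that opens the pair, using baseline values for measures taken only then, such as the spinal measurements. Read effects on change within starting state: unmet-to-met against stable unmet, and met-to-unmet against stable met. This can be done with two models or with one multinomial model. Use clustered errors as a safeguard. Interval length is an optional covariate, given the extended in-person gaps described in sections 7c and 7f. Stable met against stable unmet can still be reported as a description of durable status.

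This changes wording and analysis only and adds no visits. The cost is smaller models. With an assumed 100 patients completing three visits and half of the pairs starting met, there are 100 × 2 = 200 pairs, or 100 per model. That gives about 100 × 0.3 = 30 improvements and 100 × 0.2 = 20 worsenings, enough for only a few covariates each. The spinal measurements will also be out of date for the second pair.

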Psoriatic arthritis (PsA) is a heterogeneous autoimmune disease that occurs in one in three people with the skin disease psoriasis. PsA can cause arthritis (joint inflammation), enthesitis (tendon and ligament inflammation), sausage digits (swollen entire finger or toe), spondyloarthritis (spinal inflammation). Skin involvement by psoriasis is also highly variable in terms of psoriasis type and location. Through combined skin and musculoskeletal involvement, psoriatic disease has a significant life impact with decrease quality of life including uncomfortable symptoms, ability to participate in life and functioning. Medications used to treat PsA have sometimes an uneven effect on the various PsA manifestations where some are more effective for skin while others more effective for the joints. In this context, clinical care and treatment of PsA is a complex process which balances disease activity with medication risks and benefits as well as patient priorities. Professional PsA treatments guidelines state that PsA treatment goals are disease remission or low disease activity. Several studies to date have shown that physicians tend to overestimate remission and low disease activity in PsA patients when compared to disease activity indices. Also patients and physicians frequently do not align on perceptions of remission or low disease activity. In the proposed study we aim to identify predictors of successful treatment from a patient perspective on a range of disease measures including psoriasis, arthritis, enthesitis, dactylitis, patient reported outcomes, and laboratory assessments which are routinely collected in the clinical care of PsA. Secondary endpoints are to quantify longitudinally how stable a state of treatment success is from a patient perspective, and to define score ranges for disease measurements, including health-related quality of life measures, that correspond to treatment success from a patient perspective. **The impact of this research is that we will be able to define parameters predictive of achieving treatment success from a patient perspective, which will then inform goals of care for psoriatic arthritis.**

2. Objectives

Primary objective

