To determine predictors of reaching PsA treatment goals/treatment success (primary outcome) from a patient perspective in an academic PsA guideline-based treatment cohort. Conversely, to determine adverse predictors to reaching this desirable state. The primary outcome determination is based on the patients' report of whether they are/are not at goal with their PsA treatment.

Secondary objective(s)

To estimate the following parameters:

- A. Prevalence of patients reporting they met PsA treatment goals (successful treatment) from their perspective.

- B. Frequency and direction of longitudinal transitions between treatment goals/met not met states: 3 observations/participant.
- C. Score ranges that correspond to a status of patients' treatment goals met on a set of PsA outcome measures used in the study, including composite disease activity measures.
- D. On the same set of PsA outcome measures, meaningful change values in patients who transition longitudinally to the better and worse categories.

3. Background

Efficacy of therapeutics in PsA is incomplete, considering at most 60% of patients achieve the primary efficacy outcome in clinical trials. More so, treatment goals from the patient perspective, as well as alignment of patient opinion with index-based definitions of treatment success are part of the knowledge gap in PsA. In clinical practice, desirable treatment targets have been defined by experts as Disease Activity in Psoriatic Arthritis (DAPSA) low disease activity or remission, or Minimal Disease Activity (MDA)2. The clinical DAPSA score is computed by adding the sum of tender (out of 68) and swollen (out of 66) joints with patient global assessment and patient reported pain (each on a scale of 0-10). DAPSA remission state is defined by a score≤ 4, and DAPSA low disease activity as ≤ 14. MDA is a checklist based state defined as achieving five out of the following seven criteria: ≤ 1 swollen joint, ≤ 1 tender joint, ≤ 1 tender enthesal point, HAQ-DI score ≤ 0.5 (range 0-3), patient reported pain ≤ 1.5, patient global assessment ≤ 2, body surface area psoriasis ≤ 3%. It is of great interest to ascertain if guideline-based PsA clinical care achieves individual patient goals as articulated by patients, and to identify predictors of achieving individual patient goals from PsA treatment.

4. Study Procedures

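### Section 7c and the 7a four-category transition variable ignore the realised time between in-person visits, so pooled transition frequencies cannot be read as stability over the nominal 3-4 months

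*Combined protocol and SAP*

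**What the plan says.** The abstract names as a secondary endpoint to "quantify longitudinally how stable a state of treatment success is from a patient perspective". Secondary objective B (section 2) puts this as "Frequency and direction of longitudinal transitions between treatment goals/met not met states: 3 observations/participant".

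The nominal spacing appears twice. Section 4 says "Study visits will occur at 3-4 month intervals in conjunction with clinical care", and the inclusion criteria in section 5 require patients who "are followed every 3-4 months".

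In section 7:

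- 7a first models met status at a visit by logistic regression on disease characteristics and patient-reported variables. It then looks for predictors of a "state variable with 4 categories: unmet to met, stable met, stable unmet, met to unmet". It adds "Full visits for this study must be in-person so that the physician assessment" is complete. Time between visits is not among the named covariates.
- 7c reads "3 observations/participant Inperson Visits only: We will determine how patient states change over time to define stability of the notion of successful treatment", followed by "Interim Telemedicine visit data will be collected to fill gaps between extended in-person intervals".
- 7f attributes the long in-person gaps to COVID-19 and gives telemedicine data a general gap-filling purpose. It has no rule for the transition analysis.

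**The concern.** Whether a patient is found in a different state at the next visit depends on how long one waits. A frequency that mixes gaps of 3-4 months with longer ones therefore reflects the mix of gaps as well as the patients. A reader will naturally take the result for objective B as stability over the planned interval, and it will not be that if many gaps ran long. A change that reverses within a long gap is also missed, so the pair is counted as stable.

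The direction of the error is not fixed. If patients have similar rates and visit timing carries no information, longer gaps show more transitions. If stable patients are seen less often, that relation can weaken or reverse.

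For the 7a transition predictors the risk is conditional: they are distorted only if spacing is related to patient characteristics or state. The documents neither show nor exclude this. The first 7a analysis and the 7b prevalence do not use pairs of visits and are not affected.

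**Working it through.** The plan states no transition rate, realised interval or sample size, so there is no figure of its own to reproduce. What follows is an illustration.

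**Inputs.** From the documents: nominal interval 3-4 months and three observations, hence at most two transitions per participant. Assumed: a symmetric two-state process with rate λ = 0.03 / 0.05 / 0.08 per month; planned gaps of 3.5 months; extended gaps of 6 or 9 months; 25% or 50% of gaps extended. The reference is 4 months, the upper end of the plan.

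**Step 1. Chance of a different state after t months:** P(t) = 0.5 × (1 − exp(−2λt)).

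| t (months) | λ=0.03 | λ=0.05 | λ=0.08 |
|---|---|---|---|
| 3.5 | 9.5% | 14.8% | 21.4% |
| 4 | 10.7% | 16.5% | 23.6% |
| 6 | 15.1% | 22.6% | 30.9% |
| 9 | 20.9% | 29.7% | 38.2% |

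**Step 2. Excess of the pooled frequency over the 4-month value:** (1 − f) × P(3.5) + f × P(g) − P(4), where f is the share of extended gaps and g their length. Example for f = 0.50, g = 9, λ = 0.05: 0.5 × 14.8 + 0.5 × 29.7 − 16.5 = 5.7 points after rounding.

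| f, g | λ=0.03 | λ=0.05 | λ=0.08 |
|---|---|---|---|
| 25%, 6 months | 0.2 | 0.2 | 0.2 |
| 50%, 6 months | 1.6 | 2.2 | 2.5 |
| 25%, 9 months | 1.7 | 2.0 | 2.0 |
| 50%, 9 months | 4.5 | 5.7 | 6.2 |

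**Step 3. By direction, with unequal rates.** P(unmet to met) = a/(a+b) × (1 − exp(−(a+b)t)), with b in the numerator for the reverse direction. With assumed a = 0.07 and b = 0.03, the 4-month values are 23.1% (unmet to met) and 9.9% (met to unmet). For 25% of gaps at 6 months, 25% at 9 and 50% at 9, the excess is 0.3 / 2.8 / 8.0 points for unmet to met and 0.1 / 1.2 / 3.4 points for met to unmet.

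**Step 4. Same state at all three visits.** Two 4-month gaps: (1 − P(4))² = 79.8 / 69.7 / 58.3%. One of the gaps at 9 months: (1 − P(4)) × (1 − P(9)) = 70.7 / 58.7 / 47.2%. The process is the same in both; only the spacing differs.

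**Step 5. The 7a transition variable, conditional on imbalance.** Take a factor with no effect on transition rates, but with 50% long gaps in one group and 20% in the other. Each group has p = (1 − f) × P(3.5) + f × P(g). The spurious odds ratio for a transition is 1.16-1.18 with 6-month gaps and 1.29-1.34 with 9-month gaps. With no imbalance in spacing this distortion does not arise.

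**Step 6. Informative timing.** Suppose stable patients (λ = 0.03) are seen at 9 months and show 20.9% transitions, while less stable patients (λ = 0.08) are seen at 3.5 months and show 21.4%. Interval length then appears to have almost no effect. With equal groups the pooled value is about 21.1%, and a model standardising to 4 months on log(interval) would also give about 21%. The true 4-month average is (10.7 + 23.6)/2 = 17.2%.

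**The case against.** The strongest reply has five parts.

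- **A nominal period exists.** It is stated in sections 4 and 5, and with three observations it implies a horizon of about 6-8 months. This stands. A reader might infer that the frequency has no period at all, and the documents do not support that. The gap is that realised intervals may depart from the nominal one and the plan does not say how it will report or handle this.
- **The plan does respond to long gaps.** Interim telemedicine data are collected for that purpose, so it would be wrong to say the problem was overlooked. But 7c keeps its observations to in-person visits, no rule brings a telemedicine answer into a transition, and the documents do not confirm that the treatment-success question was asked at those visits.
- **A per-visit frequency is a legitimate descriptive quantity** in a cohort whose visits follow clinical care. True, provided the intervals are shown beside it. Under the symmetric model above, the pooled frequency differs from the probability at the mean gap by only 0.1-0.5 points with 6-month gaps and 0.4-1.8 points with 9-month gaps. Simple reporting of intervals therefore recovers most of the missing information, and no elaborate model is required.
- **Every magnitude is assumed.** Three of the four symmetric scenarios give at most 2.5 points. For 200 transitions (100 participants, also assumed) the binomial standard error at the 4-month values is about 2.2-3.0 points. This stands, and it limits how strongly the point can be put.
- **Interval adjustment can fail.** Step 6 shows this for standardisation. Stratification does not recover the cohort-wide 4-month value there either, although it does show which gaps each frequency comes from.

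**Conclusion.** The point holds in limited form. Sections 7c and 7f acknowledge extended in-person intervals, while the 7c transitions and the 7a four-category variable carry no element of realised time. As written, the answer to objective B mixes risks over different periods and cannot be read as stability over 3-4 months.

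The size is unknown. Under constant symmetric rates and uninformative timing it runs from about 0.2 to about 6 points: negligible if few gaps were extended or the extensions were short, sizeable only if many were long. With the unequal rates tried it reaches 8.0 points in one direction.

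A reader might go further and infer that the 7a predictors are biased. The documents do not support that: distortion needs spacing to be related to patient characteristics or state, and nothing in the documents establishes such a relation. Nor is the per-visit status analysis in 7a or the prevalence in 7b in question. This is a worthwhile, inexpensive improvement to a secondary endpoint, with a precautionary addition to one part of 7a.

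**What to change.** **Section 7c.** Keep in-person visits as the primary data. Report the distribution of realised in-person intervals. Give transition frequencies by direction, both overall and stratified by interval length (up to 4 months versus longer).

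**Section 7a, four-category transition analysis only.** Add time between the paired visits as a covariate, described as a precaution.

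**Telemedicine (7c and 7f).** State that these data are supplementary. If the treatment-success question was asked at telemedicine visits, use those answers only in a sensitivity analysis with a visit-mode indicator.

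**Optional.** Standardise to 4 months with a transition logistic model on log(interval), stating that this is valid only if visit timing is uninformative.

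Leave 7b and the first 7a analysis unchanged.

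**Cost.** SAP wording and visit dates; no new data collection. Limitations to state: strata may be small, with at most two transitions per participant and no sample size in the documents; timing may be informative because visits follow clinical care, which neither strata nor a covariate fully resolves; and interval length may overlap with the COVID-19 period, so the two may be hard to separate.
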